Treatment with Pembrolizumab will continue for 17 cycles (about 12 months) in the absence of (1) documented disease progression, (2) unacceptable adverse event(s), (3) intercurrent illness that prevents further administration of treatment, (4) investigator's decision to withdraw the subject, (5) subject withdrawal of consent, (6) pregnancy of the subject, (7) noncompliance with trial treatment or procedure requirements, (8) institution of alternative systemic treatment, or (9) other administrative reasons. After the end of treatment, each subject will be followed for a minimum of 30 days for adverse event monitoring (serious adverse events will be collected for up to 90 days after the end of treatment). Subjects will have post-treatment follow-up for disease status until one of the following events: (1) disease progression; (2) initiation of non-study cancer treatment; (3) withdrawal of study consent; (4) loss to follow-up or (5) death. In addition, survival status beyond the establishment of PD or initiation of subsequent therapies will be documented.

The primary objective of the trial includes determination of PFS per RECIST 1.1. Secondary objectives include OS and safety/toxicity determination as assessed by a variety of parameters of adverse events (AEs), including incidence and time to first Grade 3-5 AE. Pre-specified adverse events of clinical interest during the Pembrolizumab phase include the following events: 1) Grade \geq 3 diarrhea 2) Grade \geq 2 colitis, 3) Grade \geq 2 pneumonitis, 4) Grade \geq 3 hypo- or hyperthyroidism, 5) Grade \geq 2 hypophysitis, 6) Grade \geq 2 uveitis, and 7) Grade \geq 2 nephritis. Participation in this trial will encourage supplying tumor tissue from either a newly obtained formalin-fixed specimen (preferred) or an older formalin-fixed, paraffin-embedded specimen, from locations not radiated prior to biopsy. The specimen will be evaluated at a central laboratory facility for expression status of PD-L1 in a retrospective manner. Eligibility for the trial will not be dependent upon PD-L1 expression status, but the sponsor may amend the trial in the future if new data arise regarding the predictive value of PD-L1 expression. Any patient enrolled on the study prior to such an amendment, however, will remain on study.

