8.2 Assessing and Recording Adverse Events

An adverse event is defined as any untoward medical occurrence in a patient or clinical investigation subject administered a pharmaceutical product and which does not necessarily have to have a causal relationship with this treatment. An adverse event can therefore be any unfavorable and unintended sign (including an abnormal laboratory finding, for example), symptom, or disease temporally associated with the use of a medicinal product or protocol-specified procedure, whether or not considered related to the medicinal product or protocol-specified procedure. Any worsening (i.e., any clinically significant adverse change in frequency and/or intensity) of a preexisting condition that is temporally associated with the use of the Merck's product, is also an adverse event.

Merck product includes any pharmaceutical product, biological product, device, diagnostic agent or protocol-specified procedure, whether investigational (including placebo or active comparator medication) or marketed, manufactured by, licensed by, provided by or distributed by Merck for human use.

Phase II Pembrolizumab Reirradiation

Adverse events may occur during the course of the use of Merck product in clinical trials or within the follow-up period specified by the protocol, or prescribed in clinical practice, from overdose (whether accidental or intentional), from abuse and from withdrawal.

All adverse events will be recorded from beginning with cycle 1 of Pembrolizumab through 30 days following cessation of treatment and at each examination on the Adverse Event case report forms/worksheets. Laboratory AE's will also start being recorded beginning with cycle 1 of Pembrolizumab. The reporting timeframe for adverse events meeting any serious criteria is described in section 8.2.3.1.

Applicable reporting to DSMC will occur as follows:

On-Site subjects (this includes any subjects enrolled at other sites on an in-house study)

1. All grade 3 or higher events (AE or SAE) within five business days of knowledge.
2. All unexpected deaths within 24 hours of knowledge.
3. All others deaths within 30 days of knowledge. Deaths of subjects off-study for greater than 30 days from the last study treatment/intervention are not reportable with the following exceptions:

Study Exceptions the CTSRMC will not Approve:

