9.4 Statistical Methods

Primary Objective

1. The primary intent-to-treat analysis will estimate progression free survival from initiation of definitive therapy by the Kaplan-Meier method. Median PFS and 95% CI will be determined. A total of 41 patients will be enrolled on the study.
2. A secondary proof of principle analysis will determine the clinical benefit of adding consolidation Pembrolizumab after definitive therapy. Only patients who receive consolidation Pembrolizumab are included in this analysis. It is expected that up to 15% of enrolled patients will have progressive disease or lingering toxicity and will not start Pembrolizumab after definitive therapy. Thus we anticipate that at least 35 patients will be included.

In this proof of principle analysis, we will compare progression free survival from initiation of definitive therapy to a historical control value. We assume the median PFS for the historical control population treated with standard therapy only is 6 months and the median PFS for the patients treated with definitive therapy and consolidation Pembrolizumab is 10 months. Assuming 35 patients are enrolled over 2 years and followed for an additional 3 months, the final analysis will have 80% power to detect an improvement in median PFS assuming exponential survival and 1-sided 5% significance level.

Secondary Objectives

1. Overall survival will be estimated by the Kaplan-Meier method. Median OS and 95% CI will be determined.
2. Toxicities will be graded, categorized and tabled. For the definitive therapy phase, we will report on adverse events which are grade 3 or higher treatment-related toxicities or any grade of pneumonitis or esophagitis. For the Pembrolizumab phase, we will report all treatment-related toxicities.

Exploratory Objective

1. Biomarkers will be tested for association with PFS using log rank test for categorical biomarkers and Cox proportional hazards regression for continuous biomarkers. Biomarkers will be tested for association with graded toxicity (i.e., worse toxicity grade) for specific categories of toxicity using chi square test for categorical biomarkers and Spearman's correlation for continuous biomarkers.

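### Exploratory biomarker-toxicity tests on worst grade make no allowance for time on pembrolizumab, so a marker that only predicts PFS can look like a toxicity marker (minor; cheap to improve)

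*Combined protocol and SAP*

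**What the plan says.** Section 9.4, Exploratory Objective, states: "Biomarkers will be tested for association with graded toxicity (i.e., worse toxicity grade) for specific categories of toxicity". The method is chi-square where the marker is categorical and Spearman where it is continuous. The sentence before it uses censored-data methods for the efficacy outcome: "Biomarkers will be tested for association with PFS using log rank test for categorical biomarkers", with Cox regression for continuous markers. No significance level is given for either set of biomarker tests; the only one stated belongs to the PFS comparison ("the final analysis will have 80% power to detect an improvement in median PFS assuming exponential survival and 1-sided 5% significance level").

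Three other places set how long a patient's toxicity is observed:
- Section 3.1 continues pembrolizumab for up to 17 cycles unless progression, toxicity or another listed reason ends it.
- Section 8.2: "All adverse events will be recorded from beginning with cycle 1 of Pembrolizumab through 30 days following cessation of treatment".
- The second footnote to the flow chart in Section 7.1 gives patients who finish all 17 cycles a year of AE monitoring after treatment, and early discontinuers 30 days (90 for serious events).

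Section 3.1 also names a time-based safety measure ("including incidence and time to first Grade 3-5 AE"), but Section 9.4 does not use it for the biomarkers.

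**The concern.** The worst grade ever recorded is cumulative: the longer a patient is watched, the higher it can go. Here the length of watching is tied to the efficacy outcome, because progression generally ends the drug and the AE window closes soon afterwards. The same paragraph looks for markers that predict PFS. Any marker that does so also predicts length of toxicity observation, and can reach significance against worst grade without altering the rate at which toxicity occurs.

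At stake is interpretation. A marker such as PD-L1 could be reported as predicting both benefit and immune toxicity when the second result only reflects longer exposure and follow-up. The issue concerns pembrolizumab-phase toxicity. The reirradiation phase is short and is reported separately.

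**Working it through.** **The plan's own figure.** None exists for the biomarker tests. The nearest is the PFS power, which also supplies the sample size. Section 9.4: "It is expected that up to 15% of enrolled patients will have progressive disease or lingering toxicity" and "Thus we anticipate that at least 35 patients will be included"; 41 × 0.85 = 34.9, so 35. With uniform accrual over a = 24 months, f = 3 further months and λ = ln 2 / median, expected events are 35 × {1 − [exp(−λf) − exp(−λ(a+f))]/(λa)}. This gives 21.2 at a 10-month median and 26.6 at 6 months, averaging 23.9. Power = Φ(√23.9 × ln(10/6) − 1.645) = Φ(0.85) = 80%. The figure reproduces, and its 1-sided 5% level applies only to that test.

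**Mechanism.** If toxicity in a category occurs at a constant rate r, the chance of at least one event in a window of w months is 1 − exp(−r·w). Seventeen cycles of 21 days are 357 days; 11.8 months is used below. Take r = 0.1 per month (assumed) for every patient:
- progression 3 months after first dose: w = 3 + 1 = 4, chance 1 − exp(−0.40) = 33%;
- completer, 30-day window: w = 11.8 + 1 = 12.8, chance 1 − exp(−1.28) = 72%;
- completer, footnote window: w = 11.8 + 12 = 23.8, chance 1 − exp(−2.38) = 91%.

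The toxicity rate is identical in all three; only observation differs.

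**Rejection rates by simulation.** From the documents: 35 starters, the drug-stopping rule, the two AE windows. Assumed: the marker acts on PFS only; exponential time to progression from first dose; toxicity independent of the marker given time observed; two-sided 5% level. Set A: median 7 or 10 months, 0.5 to 2 events per patient-year, 1,500 trials per setting. Set B: median 6.5 months, 0.02 to 0.4 events per month, 4,000 trials per setting. The marker is standard normal, and hazard ratios (HR) are for PFS per SD.

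| Spearman on worst grade | Set A | Set B |
|---|---|---|
| HR 0.7, 30-day window | not run | 6-11% |
| HR 0.61, 30-day window | 7-14% | not run |
| HR 0.5, 30-day window | 10-21% | 8-28% |
| HR 0.7, footnote window | not run | 8-15% |
| HR 0.61, footnote window | 14-23% | not run |
| HR 0.5, footnote window | 21-40% | 15-41% |
| HR 0.5, front-loaded toxicity (decay constant 2.5 months), 30-day window | not run | 5-7% |

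With no PFS effect, Spearman rejects in about 5%. At mid-range toxicity rates (roughly 0.04 to 0.2 per month), the 30-day window gives about 7-9% at HR 0.7 and 10-25% at HR 0.5.

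**What shrinks it.** With a data cut 3 months after accrual, Set A gives about 6-17%. With 20 patients having marker data and that cut, HR 0.5 gives 6-10%. For a binary marker with the 30-day window, chi-square on any-versus-none rejects in 5-7% at HR 0.7, 6-11% at HR 0.5 and 8-23% at HR 0.3; chi-square on four grade levels gives 2-8% at HR 0.5 and 2-16% at HR 0.3.

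**Alternative test.** Time to first event, censored at the end of each patient's AE window, rejects in about 4-7% (Cox, Set A) and 5.0-5.9% (log-rank for a binary marker, Set B settings) in every setting run.

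**The case against.** Five points carry weight.

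- **The size is assumed.** The documents give no marker effect, toxicity rate or toxicity timing. An HR of 0.5 per SD is strong: between the 10th and 90th percentiles (2.56 SD) it means 0.5^2.56 = 0.17. At HR 0.7 the inflation is small. This stands.
- **Constant hazard drives the result.** With early-onset toxicity the inflation almost vanishes. This stands as a limit on size. It does not rescue the test, since Section 5.2 expects immune events from soon after the first dose to months after the last, and Section 5.6.1 places thyroid disorders at any point in treatment.
- **The stated timing is kinder.** Section 9.4 puts the final PFS analysis 3 months after accrual, tissue is optional, and correlative blood work awaits funding (Section 8.1.3.1.1). All of these reduce the inflation. Section 8.1.5.5 allows follow-up to 5 years, so a later biomarker analysis is also possible.
- **The association is real in one sense.** If a marker prolongs treatment and so raises cumulative worst grade, a test of association with worst grade has detected something true. A reader might infer that the test is miscalibrated for its literal null. It is not; the difficulty is that the result will be read as an effect on toxicity itself.
- **The stakes are low.** The analysis is exploratory, and no eligibility rule or primary conclusion depends on it.

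A reader might also infer that the trial could never separate a toxicity marker from a PFS marker. That is not so: dosing dates (Section 5.4), AE start and stop dates (Table 8) and grade changes (Section 8.2.4) are all recorded.

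**Conclusion.** The structural point holds as a minor one. Section 9.4 compares worst grade across marker levels without regard to exposure or observation time, and both depend on progression. The footnote window widens the gap.

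With 35 patients and an assumed two-sided 5% level, Spearman rejection for a marker that affects PFS only runs from about 5-7% (front-loaded toxicity), through about 7-9% (constant hazard, HR 0.7 per SD, 30-day window) and about 10-25% (HR 0.5 per SD, same window), to about 40% at HR 0.5 with the footnote window. It is smaller with the 3-month data cut, with fewer patients having marker data, or with the multi-grade chi-square.

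A reader might want a single multiple, such as four times the nominal level. The documents do not support one: the nominal level is itself assumed, some plausible settings show no material inflation, and stronger assumed markers exceed any such figure (20-58% at HR 0.4 per SD with the footnote window in Set B).

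**What to change.** In Section 9.4, for the pembrolizumab phase:
- Make the inferential test the time from first pembrolizumab dose to the first event in the category at or above one grade, stated in advance. Use log-rank for categorical and Cox regression for continuous baseline markers, censoring at the end of the patient's AE window (cause-specific hazard).
- Keep worst grade by marker as a descriptive summary, labelled as not adjusted for exposure.
- Leave worst grade as it is for the short reirradiation phase.

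Reconcile the AE windows in the Section 7.1 footnote and Section 8.2, so that the censoring time is defined.

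The cost is a few sentences and no new data. The downside is that the test uses one grade threshold instead of the full scale, and a high threshold will leave few events among about 35 patients. That is why the threshold should be fixed before the data are examined.

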10 ADMINISTRATIVE AND REGULATORY DETAILS

10.1 Confidentiality

10.1.1 Confidentiality of Data

By signing this protocol, the investigator affirms to the Sponsor that information furnished to the investigator by the Sponsor will be maintained in confidence, and such information will be divulged to the institutional review board, ethics review committee (IRB/ERC) or similar or expert committee; affiliated institution and employees, only under an appropriate understanding of confidentiality with such board or committee, affiliated institution and employees. Data generated by this trial will be considered confidential by the investigator, except to the extent that it is included in a publication as provided in the Publications section of this protocol.

10.1.2 Confidentiality of Subject Records

By signing this protocol, the investigator agrees that the Sponsor (or Sponsor representative), IRB/ERC, or regulatory authority representatives may consult and/or copy trial documents in order to verify worksheet/case report form data. By signing the consent form, the subject agrees to this process. If trial documents will be photocopied during the process of verifying worksheet/case report form information, the subject will be identified by unique code only; full names/initials will be masked prior to transmission to the Sponsor.

By signing this protocol, the investigator agrees to treat all subject data used and disclosed in connection with this trial in accordance with all applicable privacy laws, rules and regulations.

10.1.3 Confidentiality of Investigator Information

By signing this protocol, the investigator recognizes that certain personal identifying information with respect to the investigator, and all subinvestigators and trial site personnel, may be used and disclosed for trial management purposes, as part of a regulatory submissions, and as required by law. This information may include:

1. Name, address, telephone number and e-mail address;
2. Hospital or clinic address and telephone number;
3. Curriculum vitae or other summary of qualifications and credentials; and
4. Other professional documentation.

Consistent with the purposes described above, this information may be transmitted to the Sponsor, and subsidiaries, affiliates and agents of the Sponsor, in this and other countries, including countries that do not have laws protecting such information.

Additionally, the investigator's name and business contact information may be included when reporting certain serious adverse events to regulatory authorities or to other investigators. By signing this protocol, the investigator expressly consents to these uses and disclosures.

10.2 Compliance with Financial Disclosure Requirements

Financial Disclosure requirements are outlined in the US Food and Drug Administration Regulations, Financial Disclosure by Clinical Investigators (21 CFR Part 54). It is the Sponsor's responsibility to determine, based on these regulations, whether a request for Financial Disclosure information is required. It is the investigator's/ subinvestigator's responsibility to comply with any such request.

The investigator/subinvestigator(s) agree, if requested by the Sponsor in accordance with 21 CFR Part 54, to provide his/her financial interests in and/or arrangements with the Sponsor to allow for the submission of complete and accurate certification and disclosure statements. The investigator/subinvestigator(s) further agree to provide this information on a Certification/Disclosure Form, commonly known as a financial disclosure form, provided by the Sponsor or through a secure password-protected electronic portal provided by the Sponsor. The investigator/subinvestigator(s) also consent to the transmission of this information to the Sponsor in the United States for these purposes. This may involve the transmission of information to countries that do not have laws protecting personal data.

10.3 Compliance with Law, Audit and Debarment

By signing this protocol, the investigator agrees to conduct the trial in an efficient and diligent manner and in conformance with this protocol; generally accepted standards of Good Clinical Practice (e.g., International Conference on Harmonization of Technical Requirements for Registration of Pharmaceuticals for Human Use Good Clinical Practice: Consolidated Guideline and other generally accepted standards of good clinical practice); and all applicable federal, state and local laws, rules and regulations relating to the conduct of the clinical trial.

The investigator also agrees to allow monitoring, audits, IRB/ERC review and regulatory authority inspection of trial-related documents and procedures and provide for direct access to all trial-related source data and documents.

The investigator agrees not to seek reimbursement from subjects, their insurance providers or from government programs for procedures included as part of the trial reimbursed to the investigator by the Sponsor.

The investigator shall prepare and maintain complete and accurate trial documentation in compliance with Good Clinical Practice standards and applicable federal, state and local laws, rules and regulations; and, for each subject participating in the trial, provide all data, and, upon completion or termination of the clinical trial, submit any other reports to the Sponsor as required by this protocol or as otherwise required pursuant to any agreement with the Sponsor.

Trial documentation will be promptly and fully disclosed to the Sponsor by the investigator upon request and also shall be made available at the trial site upon request for inspection, copying, review and audit at reasonable times by representatives of the Sponsor or any regulatory authorities. The investigator agrees to promptly take any reasonable steps that are requested by the Sponsor as a result of an audit to cure deficiencies in the trial documentation and worksheets/case report forms.

The investigator must maintain copies of all documentation and records relating to the conduct of the trial in compliance with all applicable legal and regulatory requirements. This documentation includes, but is not limited to, the protocol, worksheets/case report forms, advertising for subject participation, adverse event reports, subject source data, correspondence with regulatory authorities and IRBs/ERCs, consent forms, investigator's curricula vitae, monitor visit logs, laboratory reference ranges, laboratory certification or quality control procedures and laboratory director curriculum vitae. By signing this protocol, the investigator agrees that documentation shall be retained until at least 2 years after the last approval of a marketing application in an ICH region or until there are no pending or contemplated marketing applications in an ICH region or until at least 2 years have elapsed since the formal discontinuation of clinical development of the investigational product. Because the clinical development and marketing application process is variable, it is anticipated that the retention period can be up to 15 years or longer after protocol database lock. The Sponsor will determine the minimum retention period and notify the investigator when documents may be destroyed. The sponsor also recognizes that documents may need to be retained for a longer period if required by local regulatory requirements. All trial documents shall be made available if required by relevant regulatory authorities. The investigator must consult with and obtain written approval by the Sponsor prior to discarding trial and/or subject files.

ICH Good Clinical Practice guidelines recommend that the investigator inform the subject's primary physician about the subject's participation in the trial if the subject has a primary physician and if the subject agrees to the primary physician being informed.

The investigator will promptly inform the Sponsor of any regulatory authority inspection conducted for this trial.

Persons debarred from conducting or working on clinical trials by any court or regulatory authority will not be allowed to conduct or work on this Sponsor's trials. The investigator will immediately disclose in writing to the Sponsor if any person who is involved in conducting the trial is debarred or if any proceeding for debarment is pending or, to the best of the investigator's knowledge, threatened.

In the event the Sponsor prematurely terminates a particular trial site, the Sponsor will promptly notify that trial site's IRB/IEC.

